#### **7.4.2 Engagement with the Study and PILOT Intervention**

The assessment of whether recent NFOO survivors within an ED setting are willing to engage with peer support services will be measured by (a) the number of potentially eligible patients approached (Screening Approach form; SCA) compared with the number willing to be enrolled (provided verbal consent; ENRA or ENRY form), and (b) the length of engagement and enrollment in PILOT among those willing to be enrolled and randomized to PILOT. The length of engagement will be calculated from the day of randomization to the last day a PILOT participant was assessed as “Engaged” or “Partially Engaged” on the PIL form.

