10.0 STUDY PROCEDURES

10.1 Screening

Patients will be recruited at each ED site, either in-person or via remote techniques (if needed). Study sites will operate under the MUSC policies and procedures for recruitment given the SmartIRB master reliance agreement. As such, recruitment procedures will be the same across study sites, with any differences outside of the MUSC policies being specifically stated and approved as part of local study site standard operating procedures (SOPs). Research staff will work during times to include evenings and weekends to ensure success with enrollment. Research staff will identify patients seen in the ED by screening, reviewing the EHR trackboards and by provider or TAU peer referral. Research staff will keep a log of all patients approached and the outcome of that approach (Screening and Approach Log). Potential participants identified will be evaluated by a member of the research staff for eligibility.

Patients will be stabilized per ED usual care and receive TAU per that ED site, noting that each site will have an operationalized peer support specialist system already in place in the ED which may be a part of TAU (**Figure 1**). After clinical stabilization and TAU, research staff will ask for verbal consent to complete screening forms and assessments, which will include questions about overdoses in the past 30 days, reason for the ED visit, and other items that may exclude that individual from study inclusion. Research staff will follow an approved verbal consent script which details how their information might be used/exceptions to confidentiality based on urgent medical concerns during the screening process.

Patients who appear to be eligible will then be asked about interest in the study. If the answer is yes, research staff will describe the study and if the participant remains interested and would like to continue, written informed consent will begin.

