10.2 Eligibility Confirmation and Enrollment

After the Screening Enrollment Form has been completed and the patient meets basic eligibility criteria, they will be asked to give written informed consent.

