10.3 Eligibility Confirmation, Screening, and Baseline Assessments

After screening eligibility is confirmed, the patient will be entered into the data system to complete inclusion/exclusion information, and to confirm eligibility. The enrollment procedures will be captured through a centralized process managed by the CTN Data and Statistics Center (DSC). Study patients who do not complete all screening assessments or who are otherwise found to be ineligible for participation in the study will be considered screen failures.

The site's research team will review screening assessments to determine final eligibility for randomization. In most instances screening and baseline assessments may be performed during the same visit, and randomization will occur at that same visit (typically).

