## **3.0 GENERAL ANALYSIS POPULATIONS, DEFINITIONS, AND CONVENTIONS**

### **3.1 Analysis Populations**

#### **3.1.1 Preliminary Screened Population**

The preliminary screened population consists of all participants who provided verbal consent and were evaluated for basic study eligibility criteria. Those found to be eligible at preliminary screening are captured under Segment A (ENRA form), whereas those not interested in participating or are ineligible and, if applicable, reasons for ineligibility, are captured under Segment Y (ENRY form).

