### **3.1.5 Approached Population**

The approached population consists of all individuals who were approached in the ED for possible participation in the study, including those who did and did not provide verbal consent for further assessment of eligibility.

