**Table 36: Summary of Potentially Eligible Patients Willing to be Engaged over Number of Approached**

Number of Potentially Eligible Patients Approached 	Number of Participants Willing to be Enrolled 	Results 		
		Proportion	95% Lower Confidence Limit	95% Upper Confidence Limit
N	N	X.x%	X.xx	X.xx

 The number of participants approached is captured on the Screening Approach (SCA) form.

 Willingness to be enrolled is defined as providing verbal consent and is captured on the ENRA or ENRY enrollment form.

 Results are obtained from the Wald confidence limits.

Table 37: Summary of Length of Engagement and Enrollment in PILOT								
Number of Participants Enrolled in PILOT	Average Length of Engagement 					Results 		
	Minimum	25 th Percentile	Median	75 th Percentile	Maximum	Mean (SD)	95% Lower Confidence Limit	95% Upper Confidence Limit
N	X.x					X.x (x.x)	X.xx	X.xx

Length of engagement is calculated from the day of randomization to the last day a PILOT participant was assessed as “engaged” or “partially engaged” on the PIL form.

 Results are obtained from the Wald confidence limits.

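### SAP 7.4.2 and Table 36 count verbal consent to screening as willingness to be enrolled, while SAP 7.5.2 describes written informed consent for the same proportion

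*SAP*

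**What the plan says.** Protocol 7.2 makes engagement a secondary outcome. One part compares the number of potentially eligible patients approached with the number willing to enrol. Protocol 14.1.1 lists the same item as the number accepting the intervention. Neither section gives an operational definition of willing.

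The SAP gives two definitions:

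- SAP 7.4.2 uses "the number willing to be enrolled (provided verbal consent; ENRA or ENRY form"). The Table 36 footnote repeats it: "Willingness to be enrolled is defined as providing verbal consent and is captured on the ENRA or ENRY enrollment form".
- SAP 7.5.2, which analyses the same proportion with Wald 95% limits, describes a dataset of people who did or did not give written informed consent. The variable it names is S07CNSNT from the A and Y enrolment forms, over the number approached on the SCA form.

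The consent sequence is set out elsewhere. In Protocol 10.1, "research staff will ask for verbal consent to complete screening forms and assessments". SAP 3.1.5 describes the approached population as "including those who did and did not provide verbal consent for further assessment of eligibility". Next, "Patients who appear to be eligible will then be asked about interest in the study" (Protocol 10.1). Protocol 10.2 then states: "After the Screening Enrollment Form has been completed and the patient meets basic eligibility criteria, they will be asked to give written informed consent". On forms, SAP 3.1.1 says that "those not interested in participating or are ineligible and, if applicable, reasons for ineligibility, are captured under Segment Y (ENRY form").

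Length of engagement, the other part of this outcome, has three descriptions: baseline to last meeting (Protocol 7.2); randomisation to the last Engaged or Partially Engaged rating (SAP 7.4.2 and Table 37); and randomisation to the last intervention, taken from PIENGACT and its daily counterparts with no code values named (SAP 7.5.2).

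**The concern.** Agreeing to answer screening questions is a different act from agreeing to join a randomised trial. Under 7.4.2 the numerator is everyone on ENRA or ENRY who gave verbal consent. It therefore includes people who heard about the study and were recorded as not interested, as well as people found ineligible. The table would carry a willingness label over a screening-agreement figure.

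The outcome is a declared secondary one, reported with a 95% confidence interval, in a pilot meant to inform a larger trial. A planner who read the Table 36 percentage as an enrolment yield could be misled. Two programmers could also produce different answers, one following 7.4.2 and the other the 7.5.2 description. Length of engagement carries the same risk.

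**Working it through.** The plan states no target or expected value for this proportion, so there is no figure to reproduce. The check compares the texts and orders the counts.

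**1. Sets.** Let A be the patients approached (SCA). V is those giving verbal consent to screening (ENRA plus ENRY). E is those found eligible at preliminary screening, that is, ENRA plus people on ENRY recorded as not interested rather than ineligible. W is those who signed written informed consent.

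**2. Order.** Verbal consent comes before screening. Written consent is sought only after the screening form is complete and basic criteria are met (Protocol 10.1, 10.2). So W is contained in E, E in V, and V in A: W ≤ E ≤ V ≤ A.

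**3. The two SAP percentages.** SAP 7.4.2 and Table 36 give V/A. The description in SAP 7.5.2 gives W/A. Since W ≤ V, V/A ≥ W/A. They are equal only if everyone who agreed to be screened went on to sign.

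**4. What the gap contains.** V/A − W/A = (V − W)/A. The people in V − W are those found ineligible at preliminary screening, those eligible but not interested, and those eligible who for another reason did not sign. The gap is therefore a mixture of ineligibility and refusal.

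**5. Size.** The only related planning figure is about 150 randomised (SAP 2.2.1). If that target is met, W is at least about 150. A and V are not given, so neither percentage nor their difference can be computed.

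**6. Effect of the denominator.** Because E ≤ A, W/E ≥ W/A. W/A counts as unwilling those patients who were approached, found ineligible and never asked to join. W/E does not.

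**7. Source variable.** SAP 3.1.2 places screened participants who meet criteria and gave informed consent under Segment C. SAP 7.5.2 reads A and Y, the preliminary-screening forms. What S07CNSNT records is not shown, so the programmed numerator could be V or W.

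**8. Can W be recovered elsewhere?** Tables 1 and 2 of SAP 17.1.1 have rows or columns for verbal consents, screens and randomisations, but none for signed consents. Segment C alone would undercount W: Protocol 10.3 says that patients who do not finish screening "or who are otherwise found to be ineligible for participation in the study will be considered screen failures", and some of them may already have signed. SAP 3.1.4 does identify everyone who signed, as the safety population.

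**The case against.** **Verbal consent may be deliberate.** The SAP states it in two places, and the protocol defines no rule. Protocol 2.2 and 14.1.1 also speak of willingness to engage in study procedures, on which agreement to screening has some bearing. What stands is that written consent is not the protocol's stated rule. A reader might infer that the protocol requires it, and the documents do not support that. Written consent is the choice that matches SAP 7.5.2 and the outcome's label. Keeping verbal consent would still mean correcting 7.5.2, relabelling Table 36, and explaining why people recorded as not interested count as willing.

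**Signed over approached is not a clean measure of willingness either.** Step 6 confirms this. It stands, and the fix allows for it.

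**A reader might infer that the reported percentage will be wrong.** The documents do not show that. S07CNSNT may already hold written consent, in which case the programmed result is right and only its description is wrong.

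**A reader might try to size the gap** from the predecessor programme in Protocol 4.2, where 230 of 235 approached agreed. Those people agreed to receive services outside a randomised trial. The figures give neither the verbal nor the written count here.

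**The consequence is modest.** The proportion is descriptive, with no test or threshold, and none of the four milestones in Protocol 7.4 uses it. Randomised over approached can be computed from the planned tables. A CONSORT diagram is also planned, with content not shown. All of this stands and limits the weight of the point.

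**Conclusion.** The definition in SAP 7.4.2 and the Table 36 footnote is wrong as written for an outcome labelled willingness to be enrolled, and it conflicts with SAP 7.5.2. This rests on the text alone. The direction is certain, provided the consent sequence in Protocol 10.1 and 10.2 is followed: the 7.4.2 percentage equals or exceeds the written-consent percentage. The size is unknown, and whether the programmed figure carries the gap depends on the undisclosed content of S07CNSNT. The engagement-length definitions also conflict; the size and direction of any resulting difference cannot be derived. This should be settled before programming. It does not touch the primary analysis, alpha or sample size.

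**What to change.** In SAP 7.4.2, 7.5.2 and Table 36:

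1. Use one numerator: everyone who signed written informed consent, including those who signed and later became screen failures. SAP 3.1.4 already identifies this group.
2. Name the source variable for signed consent and state what S07CNSNT records.
3. Keep the protocol's denominator, patients approached (SCA). Beside it, report the percentage among those found eligible at preliminary screening, including people on ENRY recorded as not interested rather than ineligible. Patients found ineligible and never asked are then not read as unwilling.
4. Report verbal consent separately, labelled as agreement to screening.

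For length of engagement, set one start day and one end point across Protocol 7.2, SAP 7.4.2, SAP 7.5.2 and Table 37. Protocol 7.2 ends it at the last meeting. If that is kept, name the PIENGACT codes that count as a meeting.

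The cost is SAP wording and programming, plus alignment of Protocol 7.2 if its start or end point is not the one kept. Signed consent is already needed to define the safety population. The downside is that the percentage over those approached will be the same as, or lower than, under the 7.4.2 rule.

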### **7.5 Analyses of the Secondary Outcome Measures**

#### **7.5.1 Steps Achieved on Modified SUD Cascade of Care**

The number of steps achieved along the modified SUD Cascade of Care at Day 180 will be modeled in a similar way as the primary outcome, using a Poisson regression model with fixed effect covariates for treatment, site, and stratum. Note that no baseline score covariate is included as all participants will be considered to have achieved zero steps at baseline. The template SAS code to fit this model is given below.

```
proc glimmix data = data_sec method = quad;
  class site day strata;
  model steps = trt|day site strata / dist = poisson link = log;
  random intercept / subject = participant;
run;
```

where:

- *data\_sec* is the secondary outcome dataset for the Cascade of Care,
- *steps* is the secondary outcome number of steps achieved,
- *trt* is a treatment indicator with a value of 1 indicating PILOT and 0 indicating TAU,
- *day* is the study visit (Day 30, Day 90, or Day 180),
- *site* is the participant's site, and
- *strata* is the participant's stratum level.

Assessment of model fit will be based on standard goodness-of-fit metrics (e.g., deviance), inspection of residuals; if needed, other distributional assumptions will be considered (see section 7.3).

The RR (exponentiated estimate of the treatment x day interaction at Day 180) and 95% confidence interval, with corresponding p-value from a two-sided test (type I error rate of 5%), from this model will be used to assess the effect and significance of PILOT as compared to TAU for this secondary outcome. Given this model is testing a single hypothesis, no adjustment for multiple testing will be performed.

It is possible that participants entering the trial may not have a primary diagnosis of OUD, or even SUD and, as a result, be ineligible at baseline for some steps in the SUD Cascade of Care. However, during the study a participant may endorse OUD, or some SUD, even if none were endorsed at baseline, and become eligible for these steps. The assumption made here for the prespecified analysis is that of protection/balance by randomization. That is, participants entering without OUD, or without SUD, are likely to be balanced between treatment groups due to random assignment, such that any effects would be equal between PILOT and TAU. This assumption will be assessed by comparing the frequency distribution of participants with no identified OUD or SUD at baseline (as determined via administration of the DSM-5 checklist), between treatment arms.

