14.4 Statistical Methods for Primary and Secondary Outcomes

Primary Outcome

The primary outcome of number of self-reported overdose risk behaviors at 180 days after Index ED admission, measured as the total score, will be analyzed with a longitudinal mixed effect Poisson regression model incorporating total score at earlier time points as well as 180 days. Fixed effect covariates for baseline score, treatment, days, site, stratum, and an interaction between treatment and days. Days will enter the model as a categorical covariate, as opposed to continuous, to allow greater flexibility. A random effect is included to account for correlation within each participant. The template SAS code to fit this model is given below.

```
pproc glimmix data = data;
  class site days participant;
  model risks = baseline trt|days site strat / dist = poisson link = log;
  random intercept / subject = participant;
run;
```

where data is the dataset, risks is the outcome, baseline is the participants risk behavior score at baseline, trt is a treatment indicator with a value of 1 indicating PILOT and 0 indicating TAU, days is the day number of the visit, and site and strat are variables corresponding to the participant's site and stratum level respectively.

The treatment effect of PILOT from this model will be given as a rate ratio (RR; as the exponential of the treatment and days interaction at 180 days plus the main effect of treatment) along with 95% confidence interval. This can be interpreted, conditionally, as a ratio of the mean risk behaviors for those assigned to PILOT divided by the mean risk behaviors for those assigned to TAU at 180 days, while all other variables (specifically including the baseline value) are the same. A value of 1 for the RR is the pivotal value. An RR of less than 1 would indicate less opioid risk behaviors for those assigned to PILOT compared to those assigned to TAU. A p-value will also be provided, testing whether there was a significant effect of PILOT versus TAU. If the p-value is strictly less than 0.05, there is a significant effect.

Key secondary hypotheses are this same outcome, but at 30 and 90 days, as opposed to 180 days. These will be analyzed in the same manner.

Secondary Outcomes

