A secondary outcome is the number of steps achieved along a modified SUD Cascade of Care. This will be modeled similar to the primary outcome, an over dispersed Poisson regression model with fixed effect covariates for treatment, site, and stratum. Note that no baseline score covariate is included as all participants will be considered to have achieved 0 steps at baseline. Similar to the primary outcome, a RR along with 95% confidence interval and p-value will be given from this model to determine the effect and significance of PILOT as compared to TAU.

An important point to consider is that participants entering the trial may not have a primary diagnosis of OUD, or even SUD. Because of this, some steps are not inherently eligible to them at baseline. However, during the study, the participant may endorse OUD, or some SUD if none were at baseline, and become eligible for these steps. The approach taken here for the prespecified analysis method is that of protection/balanced by randomization. Participants entering without OUD, or no SUD, are likely to be balanced between treatment groups due to random assignment to treatment group (based on baseline DSM-5 SUD diagnoses), such that the effects of this would be equal between PILOT and FORCE. Additional supportive analyses, such as looking at OUD, SUD other than OUD, and no SUD subgroups as determined at baseline, are possible to examine possible chance imbalance between PILOT and FORCE.

For the other secondary outcomes, the number of participants approached and number who were willing to engage with CPPSSs using the PILOT model, as well as percent of those approached who were willing to engage, will be summarized. A 95% confidence interval will be provided for this percent. The length of engagement with PILOT will be similarly summarized.

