**Table 34: Summary of Secondary Outcome Analysis: Steps Achieved Along a Modified SUD Cascade of Care by Treatment Arm**

Treatment Arm	Number of Participants Randomized	Results 				
		Steps Achieved at Day 180  Mean (SD)	Rate Ratio	95% Lower Confidence Limit	95% Upper Confidence Limit	p-value
TAU	N	X (X.x)	X.xx	X.xx	X.xx	0.xxx
PILOT						
Total						

 Steps achieved is collected on the following forms: HRC, SAA, MCA, DSM, UDT, and ARC

 Results are obtained from the longitudinal mixed effects model. The rate ratio and p-value result from the interaction term between treatment arm and day at Day 180.

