### 17.1.7 Supportive Analyses of the Secondary Outcome

**Table 38: Summary of Secondary Outcome Analysis: Steps Achieved Along a Modified SUD Cascade of Care by Primary Substance Use Disorder and Treatment Arm**

Primary Substance of Use 	Number of Participants Randomized	Treatment Arm		Results 			
		TAU (N =XX)	PILOT (N =XX)	Rate Ratio	95% Lower Confidence Limit	95% Upper Confidence Limit	p-value
		ORBC Score Collected at Day 180  (Mean (SD))	ORBC Score Collected at Day 180  (Mean (SD))				
Primary OUD	N	X.X (X.XX)	X.X (X.XX)	X.XX	X.XX	X.XX	0.xxx
Primary SUD other than OUD							
No SUD identified at baseline							

 Primary substance of use is identified at baseline via the DSM-5 checklist.

 Steps achieved is collected on the following forms: HRC, SAA, MCA, DSM, UDT, and ARC

 Results are obtained from the longitudinal mixed effects model. The rate ratio and p-value result from the interaction term between treatment arm, SUD subgroup, and day at Day 180.

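### SAP 7.5.1's code and rate ratio for the steps outcome conflict with its own prose and with Protocol 14.4, and the interaction alone is not the Day 180 PILOT/TAU ratio

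*SAP*

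**What the plan says.** Protocol 14.4 (Secondary Outcomes) says the steps count is modelled similarly to the primary outcome and then specifies "an over dispersed Poisson regression model with fixed effect covariates for treatment, site, and stratum". SAP 7.5.1 opens the same way for the Day 180 count, "using a Poisson regression model with fixed effect covariates for treatment, site, and stratum", but without the dispersion wording.

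The template code in SAP 7.5.1 has "model steps = trt|day site strata / dist = poisson link = log", a participant random intercept and quadrature estimation, with day defined as Day 30, 90 or 180. The input file is described only in general terms: it "is the secondary outcome dataset for the Cascade of Care". How its Day 30 and Day 90 rows are counted is not stated.

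The RR is defined as the "exponentiated estimate of the treatment x day interaction at Day 180". Footnote 2 of Table 34 repeats this: "Results are obtained from the longitudinal mixed effects model", with RR and p-value both taken from the interaction term. For the primary outcome, Protocol 14.4 defines the RR differently, "as the exponential of the treatment and days interaction at 180 days plus the main effect of treatment".

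SAP 7.6 adds only a treatment-by-subgroup interaction for the SUD subgroups. Footnote 3 of Table 38 says otherwise: "The rate ratio and p-value result from the interaction term between treatment arm, SUD subgroup, and day at Day 180".

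SAP 7.4.1 counts a step as met if it is met at any study visit and treats a missing step as not met. SAP 7.9 accordingly says the count has no missing data.

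**The concern.** Two models are specified for one outcome, and a programmer cannot follow both. The more serious part is the RR. In a model with treatment, day and their product, the interaction at Day 180 says how the treatment ratio changed since a reference visit. The stated question is whether the arms differ at Day 180. A PILOT effect present from the first visit would leave an interaction near zero on the log scale, and the table would show little or nothing.

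The stacked model also suits this outcome poorly. Under the any-visit rule the Day 180 count would contain the earlier counts, yet the model treats the three rows as independent Poisson given the intercept. At stake are the reported size and sign of the effect on steps, the width of its interval, and the effect size carried into the larger trial.

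**Working it through.** **1. The plan's own figure.** The documents give no power, mean or standard error (SE) for the steps outcome. Their only design calculation is power for the primary outcome. Simulating the stated process (4,000 runs) gave 93.1% against 93.32% (N=150, mean 3.55, RR 0.72), 79.5% against 80.08% (N=100), 85.9% against 86.92% (mean 2.8) and 83.7% against 83.57% (RR 0.76). This checks the simulation method; it says nothing about steps.

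**2. The specifications side by side.**

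| Source | Rows | Terms | Dispersion | Random effect |
|---|---|---|---|---|
| Protocol 14.4 | not stated | treatment, site, stratum | yes | none listed |
| SAP 7.5.1 prose | Day 180 count | treatment, site, stratum | none | none listed |
| SAP 7.5.1 code | Days 30, 90, 180 | treatment, day, product, site, stratum | none | participant intercept |

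**3. What the interaction estimates.** Write log RR(d) = β + γ(d), with γ = 0 at the reference visit. Then exp(γ(180)) = RR(180) / RR(reference). It equals the Day 180 ratio only if the reference visit shows no effect. The code sets no reference visit. If Day 180 itself were the reference, the result would be 1 by construction.
- One set of simulations had a Day 180 RR of 1.25. With Day 30 as reference the interaction averaged 0.94 to 0.97. This implies a Day 30 RR of about 1.25/0.97 = 1.29 to 1.25/0.94 = 1.33. A benefit would print as slight harm.
- In another set (propensity SD 0.5, no loss) the two-arm means were 2.00 at Day 30 and 3.89 at Day 180 under the null, and 2.20 and 4.33 with an effect. If TAU keeps the null means, RR(30) = 2 × 2.20/2.00 − 1 = 1.20 and RR(180) = 2 × 4.33/3.89 − 1 = 1.23. The interaction is then 1.23/1.20, about 1.02. Across the eight effect scenarios in that set, with a Day 180 RR of about 1.15 to 1.23, testing Day 180 against Day 30 rejected in 0 to 0.3% of trials.

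**4. What stacking gains.** Nothing in completeness: every participant has a Day 180 count by definition.

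**5. Why overlapping rows distort the SE.** Take cumulative counts with means 2.0, 3.2 and 4.2, no between-person variation and 75 per arm. The SD of the Day 180 log RR from a one-row analysis is √(2/(75 × 4.2)) = 0.080. The stacked fit reads carried-forward steps as person-to-person variation, with a fitted intercept SD of 0.41. Its implied SE is √((2/75) × (exp(0.41²) − 1 + 1/4.2)) = 0.106. The stacked estimate's true SD was 0.085, so 0.106/0.085 = 1.25; the simulation gave 1.24.

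**6. Simulated size.** Assumed, because the documents give no values: N=150, Day 180 mean about 2.5 to 4.2 steps, logit propensity SD 0 to 2, and 0 to 30% of participants with no post-baseline data (counted as not met). There were 800 null trials per scenario. The contrast is main effect plus interaction at Day 180, with cumulative rows. SE/SD is the mean model SE over the empirical SD; null rejection at nominal 5% is in brackets.

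| Scenario | Stacked SE/SD |
|---|---|
| Ten steps, no loss, propensity SD 0 / 0.5 / 1 / 1.5 / 2 | 1.46 (0.3%) / 1.32 (1.1%) / 1.17 (1.8%) / 1.10 (3.0%) / 1.07 (3.3%) |
| 10% loss, propensity SD 1 / 2 | 1.07 / 1.02 |
| 20–30% loss | 0.98–1.02 (4.5–5.2%) |
| Unbounded process, frailty variance 0 / 0.2 / 0.5 / 1 | 1.24 (1.9%) / 1.17 (2.1%) / 1.08 (3.7%) / 1.01 (4.0%) |

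The one-row over-dispersed model gave 0.95–1.04 (3.4–6.6%) in all 15 scenarios. Under heavy loss the stacked SE is about right, but its estimate is noisier: SD 0.20 against 0.14 at 20% loss.

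A second set of 24 scenarios, with a different generator, gave 1.16–1.38 without dropout and 1.05–1.17 with 25% dropout, against 0.97–1.03 for the one-row model. At very strong heterogeneity it gave 0.99–1.05, and one further scenario gave 0.88.

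**7. Visit-specific rows.** Without dropout, SE/SD was 1.04–1.10 in one set and 1.07–1.23 in the other. With 25% dropout it was 0.90–0.93 (null rejection 6.5–9.2%).

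**8. Power at Day 180, proper contrast, cumulative rows.** At an RR of about 1.20–1.23 and propensity SD 0, 0.5, 1: stacked 82%, 67%, 44% against one-row 97%, 90%, 64% with no loss; 23.0%, 21.7%, 17.7% against 46.0%, 43.5%, 32.8% with 20% loss.

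**9. Plain one-row Poisson.** Without a dispersion term, null rejection rose to 27% in the ten-step scenarios and 43% at frailty variance 1.

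**The case against.** The strongest reply is that both documents call the steps model similar to the primary one, which is a longitudinal mixed Poisson model, and that a random intercept is itself a way to allow over-dispersion. This stands in part: one row per participant is inferred from the covariate list, not stated. A reader might go further and say the SAP overrides an explicit one-row Protocol model; the text does not support that. On the other side, both documents name day, treatment by day and the participant effect explicitly for the primary outcome and omit all three from the steps prose. Even if a longitudinal model was intended, the RR sentence still names the wrong contrast.

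Second, SAP 7.5.1 sends misfit to SAP 7.3, which checks for under-dispersion and lists generalized Poisson in step 4a. In a small run (150 null trials per scenario) that model brought SE/SD from 1.38 to 1.04 and from 1.27 to 0.96. But it comes after negative binomial, which can only add variance, it is only something that may be fitted, and it was unstable under strong heterogeneity or dropout. It is a partial, optional remedy, and it does not touch the RR definition.

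Third, the SE results rest on an unstated row rule and assumed rates. The 24-scenario set also nests Step 3 within Step 2 and Step 9 within Step 8, which the definitions do not require: the recall periods differ (past month against past 90 days), and Step 8 concerns the primary SUD while Step 9 concerns any substance. The Protocol expects follow-up to be difficult, so the no-dropout figures are the less relevant ones. All of this stands.

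Finally, this is an unpowered secondary outcome in a pilot, and the SE error is mostly conservative. That limits the severity, but does not excuse an RR that answers another question.

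**Conclusion.** The point holds. SAP 7.5.1 contradicts itself and the Protocol 14.4 covariate list, drops the dispersion term, and names an interaction that is not the Day 180 PILOT/TAU ratio. The Table 38 footnote adds a three-way term that SAP 7.6 does not specify. These conclusions rest on the text and simple algebra, without any simulation.

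The SE finding is conditional. If the Day 30 and Day 90 rows are cumulative, the stacked SE for the Day 180 effect tends to be too large: SE/SD roughly 1.0 to 1.4, largest with no dropout and near 1 with heavy loss or strong heterogeneity. A reader might infer that the interval is certainly too wide. The documents do not support that, because they never define those rows, and visit-specific rows with dropout gave the opposite direction. Nor is inflated false-positive error shown for the plan with its fallback: a one-row plain Poisson model followed by the SAP 7.3 negative binomial step rejected in 2.3 to 5.8% of null trials. The power losses depend on the assumed rates, and with dropout they partly reflect a less efficient estimate rather than a wrong SE.

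This should be corrected before analysis; confidence in the size of the SE error is moderate.

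**What to change.** Use one row per participant, the Day 180 count, in a Poisson model with log link and treatment, site and stratum, with an estimated dispersion or a robust variance. Remove day, the random intercept and the quadrature option. Report the RR as the exponentiated treatment coefficient with its 95% interval. Restore the dispersion wording in the prose of SAP 7.5.1, rewrite the RR sentence and the Table 34 footnote to match, and align the Table 38 footnote with the treatment-by-subgroup term of SAP 7.6. Do not just delete the extra terms: plain Poisson without a dispersion term errs the other way when counts are over-dispersed.

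If the longitudinal model is kept, justify it, state whether the Day 30 and Day 90 rows are cumulative or visit-specific, and report the Day 180 simple effect (main effect plus interaction) through an explicit contrast.

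The cost is a shorter SAS call, a few words of prose, one RR sentence and two footnotes. No new data are needed.
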